8.9 Withdrawal of Patients from the Study

Patients must be withdrawn from the study for any of the following:

- Withdrawal of consent
- The patient is unwilling or unable to comply with the protocol
- The patient meets any of the Exclusion Criteria (see [Section 5.2](#)) after enrolling in the study that in the opinion of the Investigator represents a safety risk to the patient

Other reasons for withdrawal of patients from the study might include:

- At the discretion of the Investigator for medical reasons
- At the discretion of the Investigator or Sponsor for noncompliance
- Significant protocol deviation

All efforts will be made to complete and report the observations as thoroughly as possible up to the date of withdrawal. All information, including the reason for withdrawal from study, must be recorded in the eCRF.

Any patient who withdraws consent to participate in the study will be removed from further treatment and study observation immediately upon the date of request. These patients should be encouraged to complete the ET visit (Week 53 visit assessments) and observations at the time of withdrawal ([Appendix A](#)).

For patients withdrawn for reasons other than withdrawal of consent every effort should be made to complete the ET visit (Week 53 visit assessments) and observations at the time of withdrawal ([Appendix A](#)).

8.10 Concomitant Therapy and Procedures

The use of concomitant therapies or procedures defined below must be recorded on the patient's eCRF. AEs related to administration of these therapies or procedures must also be documented on the appropriate eCRF.

8.10.1 Concomitant Therapy

A concomitant therapy is any non-protocol specified drug or substance (including over-the-counter medications, herbal medications and vitamin supplements) administered from the time the patient has signed the informed consent at Screening to the end of the post-treatment follow-up period.

Allowed Concomitant Therapy

Use of the following is allowed only if the patient has been on a stable regimen for at least 4 weeks prior to screening and is planned to remain on a stable regimen through the end of the post-treatment follow-up period:

- Lipid lowering drugs (statins, ezetimibe, 0 inhibitors, niacin, fibrates, fish oil, other products containing omega-3 fatty acids (including OTC preparations)
 - The timing of PCSK9 inhibitor and study drug administration should be kept consistent with respect to lipid assessments. The first dose of ISIS 678354 (i.e., Study Day 1) will be scheduled for one day ahead of the next planned PCSK9 inhibitor injection to establish a regular time span between the two medications. PCSK9 inhibitors should be administered one day after administration of the study drug for the whole duration of the study treatment.
- Anti-platelet therapies
- Testosterone, estrogens, progesterone, growth hormone, or progestins.

Disallowed Concomitant Therapy

Use of the following is disallowed:

- Warfarin and other vitamin K antagonists, direct thrombin inhibitors or Factor Xa inhibitors
- Other experimental agents during the study including investigational drug, biological agent, or device within 1 month of Screening, or 5 half-lives of investigational agent, whichever is longer. This includes marketed agents at experimental dosages
- Treatment with any non-Ionis oligonucleotide (including siRNA) at any time or prior treatment with an Ionis oligonucleotide or siRNA within 9 months of Screening. Patients that have previously received only 1 dose of an Ionis oligonucleotide as part of a clinical study may be included as long as \geq 4 months has elapsed since dosing

- Lipoprotein apheresis

Patients should consult with the Site Investigator or designee prior to initiating any new medication, including non-prescription or herbal compounds or any other non-drug therapy.

8.10.2 Concomitant Procedures

A concomitant procedure is any therapeutic intervention (e.g., surgery/biopsy, physical therapy) or diagnostic assessment (e.g., blood gas measurement, bacterial cultures) performed between screening and the end of the post-treatment follow-up period.

8.11 Treatment Compliance

Compliance with treatment dosing is to be monitored and documented by the Study Center staff and recorded in the eCRF.

Patients or Study Center Staff will record treatment administered in a dosing diary that will be reviewed by Study Center staff and entered into the eCRF.

8.12 Safety Monitoring Compliance

Compliance with safety monitoring requirements and treatment stopping rules must be documented by the Study Center staff.

Patients and the Study Investigators are required to adhere to a strict program of monitoring requirements and treatment stopping rules as described in [Section 6.2.1](#), [Sections 8.5.1-8.5.8](#), and [Sections 8.6.1-8.6.4](#).

While on treatment patients will be required to have platelet counts every 14 days (± 2 days) for the duration of the study and must not receive Study Drug without an interpretable platelet count result in the prior 2 weeks, in which case the Investigator must contact the patient to hold dosing until a new platelet count is obtained and reviewed, and will document this contact.

While on treatment patients will also be required to have renal function testing and assessment of biomarkers of renal damage every 14 days (± 2 days) for the first 3 months of the study treatment, and monthly thereafter during the treatment period. In such a case, the Investigator must contact the patient to hold dosing until these or new tests are obtained and reviewed.

Adherence to the program will be closely monitored by the Sponsor, and patients and trial sites that are unable or unwilling to comply with this important risk mitigation program will be discontinued from the study.

Patients should be informed of the possibility and risks of a reduction in platelet count, and of potential hepatic and renal risks, and the importance of adherence to the monitoring program. Any case of a platelet count reduction to levels below 50,000/mm³, or any event meeting renal stopping rules criteria described in [Section 8.6.2](#) are considered adverse events of special interest and should be reported in an expedited fashion to the Sponsor.

9. SERIOUS AND NON-SERIOUS ADVERSE EVENT REPORTING

9.1 Sponsor Review of Safety Information

Safety information will be collected, reviewed, and evaluated by the Sponsor or designee in accordance with the Safety Management Plan throughout the conduct of the clinical trial.

9.2 Regulatory Requirements

The Sponsor or designee is responsible for regulatory submissions and reporting to the Investigators of suspected unexpected serious adverse reactions (SUSARs) per the International Conference on Harmonization (ICH) guidelines E2A and ICH E6. Country-specific regulatory requirements will be followed in accordance with local country regulations and guidelines.

Institutional Review Boards (IRB)/Independent Ethics Committees (IEC) will be notified of any SAE according to applicable regulations.

In addition to the Investigator's assessment of relatedness, the Sponsor or designee will evaluate the available information and perform an independent assessment of relatedness. While the Sponsor may upgrade an Investigator's decision it is not permissible to downgrade the Investigator's opinion for the purposes of determining whether the SAE meets the definition of a SUSAR.

Appropriate personnel at the Sponsor or designee will unblind SUSARs for the purpose of regulatory reporting. The Sponsor or designee will submit SUSARs to Regulatory Agencies in blinded or unblinded fashion according to local law.

9.3 Definitions

9.3.1 *Adverse Event*

An *adverse event* (AE) is any unfavorable and unintended sign (including a clinically-significant abnormal laboratory finding, for example), symptom, or disease temporally associated with the study or use of investigational drug product, whether or not the AE is considered related to the investigational drug product.

9.3.2 *Adverse Reaction and Unexpected Adverse Reaction*

Adverse reaction: All untoward and unintended responses to an investigational medicinal product related to any dose administered.

Unexpected adverse reaction: an adverse reaction, the nature or severity of which is not consistent with the applicable product information (e.g., Investigator's Brochure for an unauthorized investigational product or summary of product characteristics for an authorized product).

9.3.3 *Serious Adverse Event (SAE)*

A SAE is any AE that in the view of either the Investigator or Sponsor, meets any of the following criteria:

- Results in death

- Is life threatening, that is, poses an immediate risk of death at the time of the event
- An AE or adverse reaction is considered “life-threatening” if, in the view of either the Investigator or Sponsor, its occurrence places the patient at immediate risk of death. It does not include an AE or adverse reaction that, had it occurred in a more severe form, might have caused death
- Requires inpatient hospitalization or prolongation of existing hospitalization
- Results in a persistent or significant incapacity or substantial disruption of the ability to conduct normal life functions
- Results in a congenital anomaly or birth defect in the offspring of the patient (whether the patient is male or female)
- Important medical events that may not result in death, are not life-threatening, or do not require hospitalization may also be considered serious when, based upon appropriate medical judgment, they may jeopardize the patient and may require medical or surgical intervention to prevent one of the outcomes listed in this definition. Examples of such medical events include allergic bronchospasm requiring intensive treatment in an emergency room or at home, blood dyscrasias or convulsions that do not result in inpatient hospitalization, or the development of drug dependency or drug abuse

9.3.3.1 *Adverse Events of Special Interest*

For the purpose of this study severe reductions in platelet count < 50,000 mm³ as well as any event meeting renal stopping rules criteria described in [Section 8.6.2](#) are considered as AE of special interest and should be subject to expediting reporting to the Sponsor following the same requirements as for SAE reporting ([Section 9.4.1](#)).

9.4 Monitoring and Recording Adverse Events

Any pre-existing conditions or signs and/or symptoms present in a patient prior to the start of the study (i.e., before informed consent) should be recorded as Medical History and not recorded as AEs unless the pre-existing condition worsened. The Investigator should always group signs and symptoms into a single term that constitutes a **single unifying diagnosis** if possible.

9.4.1 *Serious Adverse Events/Adverse Events of Special Interest*

In the interest of patient safety, and in order to fulfill regulatory requirements, all SAEs and AEs of special interest (regardless of their relationship to Study Drug) should be reported to the Sponsor or designee within 24 hours of the Study Center’s first knowledge of the event. The collection of SAEs will begin after the patient signs the informed consent form and stop at the end of the patient’s follow-up period. An Initial Serious Adverse Event Form should be completed and a copy should be emailed or faxed to the Sponsor or designee. The contact information for reporting SAEs is as follows:

Attention: [REDACTED]

Email: [REDACTED]

Fax: [REDACTED]

Detailed information should be actively sought and included on Follow-Up Serious Adverse Event Forms as soon as additional information becomes available. All SAEs will be followed until resolution during the study period. SAEs that remain ongoing past the patient's last protocol-specified follow-up visit will be evaluated by the Investigator and Sponsor. If the Investigator and Sponsor agree the patient's condition is unlikely to resolve, the Investigator and Sponsor will determine the follow-up requirement.

All SAEs considered treatment-related, as defined in [Section 9.4.3.1](#), will be reported by the Sponsor to the DSMB as described in [Section 3.6](#).

9.4.2 Non-Serious Adverse Events

The recording of non-serious AEs will begin after the patient signs the informed consent form and will stop at the end of the patient's follow-up period. The Investigator will monitor each patient closely and record all observed or volunteered AEs on the Adverse Event Case Report Form.

9.4.3 Evaluation of Adverse Events (Serious and Non-Serious)

The Investigator's opinion of the following should be documented on the Adverse Event Case Report Form:

9.4.3.1 Relationship to the Study Drug

The event's relationship to the Study Drug (ISIS 678354 or placebo) is characterized by 1 of the following:

- **Related:** There is clear evidence that the event is related to the use of Study Drug, e.g., confirmation by positive re-challenge test
- **Possible:** The event cannot be explained by the patient's medical condition, concomitant therapy, or other causes, and there is a plausible temporal relationship between the event and Study Drug (ISIS 678354 or placebo) administration
- **Unlikely/Remote:** An event for which an alternative explanation is more likely (e.g., concomitant medications or ongoing medical conditions. For reporting purposes, Unlikely/Remote will be grouped together with Not Related)
- **Not Related:** The event can be readily explained by the patient's underlying medical condition, concomitant therapy, or other causes, and therefore, the Investigator believes no relationship exists between the event and Study Drug

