5.1 Inclusion Criteria

1. Must have given written informed consent (signed and dated) and any authorizations required by local law and be able to comply with all study requirements
2. Males or females aged ≥ 18 and ≤ 80 years old at the time of informed consent
3. a. Clinical diagnosis of CVD (defined as documented coronary artery disease, stroke, or peripheral artery disease; refer to [Section 3.1](#)), OR
b. High risk for CVD defined as:
 - o Type 2 Diabetes Mellitus requiring treatment, and
 - o Age ≥ 50 years, and
 - o at least one additional CV risk factor:
 - men ≥ 55 years of age and women ≥ 65 years of age, or
 - current cigarette smoker, or stopped smoking within 3 months prior screening, or
 - hypertension requiring antihypertensive treatment
4. Fasting serum TG ≥ 200 mg/dL (≥ 2.3 mmol/L) and ≤ 500 mg/dL (≥ 5.7 mmol/L) at Screening. If the fasting TG value at Screening is < 200 mg/dL (< 2.3 mmol/L) but ≥ 150 mg/dL (≥ 1.7 mmol/L) one additional test may be performed in order to qualify
5. Fasting TG ≥ 200 mg/dL and ≤ 500 mg/dL at Qualification visit. If fasting TG is < 200 mg/dL but ≥ 150 mg/dL one additional test may be performed in order to qualify
6. Must be on standard-of-care preventative therapy for their known CVD risk factors (e.g., hyperlipidemia, hypertension, diabetes)
7. Patients on the following medications must be on a stable regimen for at least 4 weeks prior to Screening and expected to remain on a stable regimen through the end of the post-treatment follow-up period:
 - a. Lipid lowering drugs (statins, ezetimibe, PCSK9 inhibitors, niacin, fibrates, fish oil or other products containing omega-3 fatty acids including OTC preparations)
 - b. Antiplatelet drugs
 - c. Testosterone, estrogens, progesterone, growth hormone or progestins
8. Females: must be non-pregnant and non-lactating and either:
 - a. Surgically sterile (e.g., tubal occlusion, hysterectomy, bilateral salpingectomy, bilateral oophorectomy);
 - b. Post-menopausal (defined as 12 months of spontaneous amenorrhea in females > 55 years of age or, in females ≤ 55 years, 12 months of spontaneous amenorrhea without an alternative medical cause and FSH levels in the postmenopausal range for the laboratory involved);

- c. Abstinent* or,

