10.1.4 Dose Selection

Dose selection for the further development will be based on the following efficacy and safety considerations; more than 1 dose may meet these criteria. An effective dose, or dose regimen, will be one that achieves a clinically-meaningful reduction in serum TG levels. Safety will be evaluated on the basis of incidence of expected and unexpected treatment-related SAEs, and other specific safety considerations including the incidence of platelet reductions.

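### The protocol's causality scale has no category for an event that Study Drug and another cause explain about equally well, so such events may be under-counted as treatment-related

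*Combined protocol and SAP*

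**What the plan says.** Protocol 9.4.3.1 states that the relationship of an event to Study Drug "is characterized by 1 of the following". The four categories are:

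- Related is reserved for one situation: "There is clear evidence that the event is related to the use of Study Drug, e.g., confirmation by positive re-challenge test".
- The category Possible has two conditions, both needed: "The event cannot be explained by the patient's medical condition, concomitant therapy, or other causes, and there is a plausible temporal relationship". The link in time is with dosing.
- The category Unlikely/Remote is described as "An event for which an alternative explanation is more likely". The section adds: "For reporting purposes, Unlikely/Remote will be grouped together with Not Related".
- The last category, Not Related, applies when another cause readily explains the event and, for that reason, the investigator believes that Study Drug played no part.

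No tie-break is given for an event that sits between these descriptions.

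The category is used in three places.

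- Protocol 9.4.1 has the sponsor report to the DSMB "All SAEs considered treatment-related, as defined in" 9.4.3.1.
- Protocol 10.1.4, repeated in the synopsis under Statistical Considerations, says of dose selection: "Safety will be evaluated on the basis of incidence of expected and unexpected treatment-related SAEs". It then adds other safety considerations, and names platelet reductions among them.
- SAP 3.7.2 tabulates related TEAEs and related treatment-emergent SAEs, counting Related, Possible and a missing entry as related.

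On the population, inclusion criterion 3 requires cardiovascular disease, or treated type 2 diabetes with age of at least 50 years and a further risk factor. Criterion 6 reads "Must be on standard-of-care preventative therapy for their known CVD risk factors".

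**The concern.** A causality scale should have a place for the commonest difficult case: the timing fits the drug, but something else could also have caused the event. Here Possible is closed to that case, because it requires that nothing else can explain the event. Neither of the two lower categories describes the case either.

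The trial population makes this more than a curiosity. Bleeding in a patient on an antiplatelet drug, an aminotransferase rise in a patient on a statin, or a cardiac event in a patient with coronary disease each has a candidate explanation other than Study Drug. The protocol's own Phase 1 summary (2.3.4) shows the pattern: two subjects had ALT above 3 x ULN reported as treatment-related, and both had a history of ALT elevation. If that history counts as an explanation, 9.4.3.1 would not allow Possible for such a case. The example is limited, because these were not reported as related SAEs and the Phase 1 causality definitions are not in the documents.

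At stake are three counts that rest on the category, including the first safety criterion named for dose selection. With 25 patients per cohort randomised 4:1, each regimen has 25 x 4/5 = 20 active patients, so one or two recoded SAEs can change the picture for a regimen.

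**Working it through.** The plan gives no figure to reproduce. The check is a logical one, followed by a trace of where the category is used.

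**Step 1. Apply the four definitions to one test event.** The event has plausible timing, no re-challenge or other clear evidence, and an alternative cause that is about as likely as Study Drug.

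- Related fails, because there is no clear evidence.
- Possible fails. Its timing condition is met, but its other condition is not, since another cause can explain the event.
- Unlikely/Remote fails, because the alternative is not the more likely one.
- Not Related is met in its first half (another cause readily explains the event) and fails in its second (the investigator does not believe that there is no relationship).

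No category fits, yet one must be chosen. Two of the four are non-causal and are reported as one group. Someone who takes the Possible wording at face value, and lacks the evidence for Related, has only those two left.

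**Step 2. Trace the consequences of a non-causal code.**

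- Related-SAE reporting to the DSMB (protocol 9.4.1): the event is not included.
- Treatment-related-SAE element of dose selection (10.1.4 and synopsis): the event is not counted.
- SAP 3.7.2 related-TEAE and related-SAE tables: the event is not counted. A blank entry would be counted, so an unanswered question is handled more conservatively than a considered judgement that either cause is plausible.
- SUSAR assessment (9.2): not lost. The sponsor assesses relatedness independently and may upgrade the investigator's call, but may not downgrade it. All SAEs reach the sponsor within 24 hours whatever their assessed relationship (9.4.1).
- Wider DSMB review (synopsis, protocol 3.6, SAP 2.4.2): not lost. The synopsis describes review of single events as well as aggregate data, with no causality filter.
- Platelet, liver, renal and bleeding summaries (protocol 10.1.3, SAP 3.7.2.3 and 3.7.4): not lost.
- All-TEAE and all-SAE tables (protocol 10.6.2.1, SAP 3.7.2): not lost.

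**Step 3. Size.** The documents give no event rates by causality, so the under-count cannot be calculated. A purely illustrative calculation shows how sensitive a count in 20 patients would be. Let r be the assumed proportion of patients with a drug-caused SAE, and a the assumed share of those events that also have another possible explanation. Assume that every event in that share is coded non-causal. The chance that at least one related SAE appears in a regimen is

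P = 1 - (1 - r(1 - a))^20.

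For r = 0.10 and a = 0.5 this is 1 - 0.95^20 = 0.642. The full set is:

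| r | a = 0 | a = 0.5 | a = 0.7 | a = 0.9 |
|---|---|---|---|---|
| 0.10 | 0.878 | 0.642 | 0.456 | 0.182 |
| 0.05 | 0.642 | 0.397 | 0.261 | 0.095 |

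Both r and a are assumptions without support in the documents. The formula also takes the miscoding as certain, which is the very point in doubt.

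**The case against.** A reader might infer that such events default to Not Related and so disappear from the SUSAR, DSMB and dose-selection counts. The documents do not support that. No text sets a default, and Not Related itself needs a belief that there is no relationship. The push towards a non-causal code is an inference from the narrow wording of Possible and the joint reporting of the two lower categories. The routes in Step 2 that do not depend on the investigator's category keep the events in view.

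A reader might also infer that related SAEs are the sole safety criterion for choosing a dose. They are not: 10.1.4 sets no threshold and goes on to other safety considerations, including platelet reductions.

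Nor is Possible unreachable in this population. Lipid-lowering and antiplatelet drugs must have been stable for at least 4 weeks before Screening, and ALT or AST above 2 x ULN is an exclusion. A new ALT rise on a long-stable statin is therefore not automatically explained by the statin.

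These objections stand, and they limit the consequence to three counts. They do not close the gap in the definitions. They also leave the named criterion in 10.1.4 as it is. The sponsor's right to upgrade is stated for deciding whether an SAE is a SUSAR; nothing says that it feeds the SAP tables of related events.

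**Conclusion.** The wording is wrong as written, and the severity is minor. Followed literally, 9.4.3.1 leaves an event with two about equally plausible causes without a category and steers it to the non-causal side. Such events may be under-counted in the related-SAE reports to the DSMB, in the treatment-related-SAE element of dose selection and in the SAP related-event tables.

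This rests on two assumptions: that investigators apply the Possible wording literally, and that competing explanations occur with some frequency in this population. The second is likely from the entry criteria, but the documents do not quantify it. The size of the under-count is unknown, and the probabilities in the table show sensitivity only. They do not predict this trial's counts or any effect on the dose chosen.

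**What to change.** 1. In 9.4.3.1, redefine Possible as an event with a plausible temporal relationship for which Study Drug cannot be excluded as a cause, whether or not another explanation exists. Keep Unlikely/Remote for events where the alternative is more likely. A tie then falls under Possible.
2. In 10.1.4 and the synopsis, base the SAE element of dose selection on all treatment-emergent SAEs per regimen against pooled placebo. Keep the treatment-related subset as supportive, and leave the other safety considerations unchanged. In a randomised, blinded trial this comparison needs no event-by-event causality judgement, and it holds for events already coded under the present wording.

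The cost is revised text in the protocol and the CRF guideline and a short memo to sites. No new data or tables are needed, since SAP 3.7.2 already plans both sets. The downside is that somewhat more events will be coded Possible in all arms, including placebo. The all-SAE comparison will also include background events, which is the reason to keep the related subset beside it.
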